#### **6.6.4. Subgroup Analyses of Specified Endpoints**

The subgroups may include but are not limited to,

- Age group ( $\leq 16$  years,  $> 16$  years),
- Race (White, Others),
- Corticosteroids use (Deflazacort, Prednisone/Prednisolone).
- Baseline PUL level ( $\leq$  Median,  $>$  Median)
- Baseline PUL entry Item A score ( $=1$ ,  $>1$ )
- Baseline PUL entry Item A score (2-5, 1 or 6)
- Regional subgroups:
  - US, Non-US
  - China, Non-China

The primary endpoint PUL will be repeated for relevant and appropriate subgroups. If linear assumption was met, the RCM linear regression model as described in [Section 6.6.1.1](#) will be performed for subgroup analysis; otherwise, MMRM model as described in [Section 6.6.1.2.1](#) will be performed. Secondary endpoints ppFVC, Mid-level of PUL, grip strength, and LVEF will also be analyzed by subgroups.

If subjects who took the prohibited medications constitute to more than 10% of the population, then the subgroup analysis – with or without prohibited medications will be performed.

The LSMeans of treatment difference and corresponding 95% CI will be presented in a forest plot.

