5.2.2. Prohibited Concomitant Medications

Prohibited medications include any other (approved or investigational) agents for the treatment of DMD. The list of prohibited concomitant medications for treatment of DMD includes, but is not limited to, the following:

- eteplirsen (EXONDYS 51)
- ataluren
- golodirsen (VYONDYS 53)
- casimersen (AMONDYS 45)

Questions about concomitant medications should be discussed with the Sponsor Medical Monitor or designee. Patients who are on any approved therapy for DMD should not discontinue the therapy to be eligible for the study. However, if their approved therapy is discontinued for other reasons, they could be considered for participation in this study if they meet all eligibility criteria.

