### **5.2.3. Per-Protocol Set (PPS)**

The per-protocol set will be defined as all randomized subjects who completed at least 24 doses of treatment, with baseline and at least one post-baseline PUL assessments, did not early terminated from treatment or study, and no major protocol deviation(s) that significantly impact efficacy analyses.

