## **6.2. Important Protocol Deviations**

Important protocol deviations of interest may include, but are not limited to, the following:

- Entry Deviation: Subjects who entered the study, but did not meet inclusion/exclusion criteria;
- Withdrawal Deviation: Subject met withdrawal criteria during the study but was not withdrawn;
- Dosing Deviation: Subject received the wrong treatment or incorrect dose; including incorrect timing of a dose; or subjects who missed more than 10% doses of prescribed study medication during the overall treatment period;
- Prohibited Medication Deviation: Subject received disallowed concomitant medications or non-drug therapy.

All above protocol deviations will go through the medical review process.

A subset of pre-specified important protocol deviations will be defined as major protocol deviations and subjects with major protocol deviations will be excluded from PPS analysis. The number and percentage of subjects with important protocol deviations will be categorized and tabulated as appropriate for the ITT population. COVID-19 related important protocol deviations will be summarized separately. All protocol deviations will be finalized prior to database lock and unblinding.

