### **6.6.1.1. Primary Analysis with the Random Coefficient Model (RCM)**

#### **6.6.1.1.1. Estimand Strategy**

The primary estimand is intended to provide a population level estimate of the treatment effect of the pamrevlumab on a continuous endpoint, regardless of participant compliance with the IP dosing. Treatment policy strategy will be implemented, which means all observed measurements after randomization will be used in the primary analysis.

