#### **6.6.1.1.3. Intercurrent Event Handling**

Treatment discontinuation (such as due to adverse event, lost to follow-up, withdrawal by subject, physician decision, protocol deviations, etc.): Missing data will be implicitly imputed under missing at random assumption.

Death: The worst postbaseline score of all patients in the mITT population would be used to impute all missing values due to death. Missing study day will be imputed as target day of the corresponding analysis visit.

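### Apart from the per-protocol analysis, prohibited DMD drug use is examined only by a subgroup split on post-randomisation use, behind a pooled 10% trigger that ignores imbalance between arms

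*SAP*

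**What the plan says.** Protocol section 5.2.2 defines the class broadly: "Prohibited medications include any other (approved or investigational) agents for the treatment of DMD".

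The primary estimand follows a treatment policy strategy (SAP 6.6.1.1.1), under which "all observed measurements after randomization will be used in the primary analysis". SAP 6.6.1.1.3 names two intercurrent events. For treatment discontinuation, "Missing data will be implicitly imputed under missing at random assumption"; for death, a worst-score rule applies. A subject who starts another DMD drug and stays on study drug falls under neither, so the scores simply count.

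Three other places bear on such use:

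- SAP 6.6.4, among the subgroup analyses: "If subjects who took the prohibited medications constitute to more than 10% of the population, then the subgroup analysis – with or without prohibited medications will" go ahead. It does not say which analysis set the percentage refers to, or over what period use counts.
- SAP 6.2 lists, as one kind of important deviation, "Prohibited Medication Deviation: Subject received disallowed concomitant medications or non-drug therapy". A subset of important deviations, not specified in the SAP, is classed as major, and "subjects with major protocol deviations will be excluded from PPS analysis". The per-protocol definition (SAP 5.2.3) correspondingly requires "no major protocol deviation(s) that significantly impact efficacy analyses". The primary endpoint is analysed in that set whatever the level of use (SAP 6.6.1.2.7).
- SAP 6.4 plans a descriptive summary of concomitant DMD medications.

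**The concern.** Another DMD therapy could mask a pamrevlumab effect on PUL if taken mostly on placebo, or mimic one if taken mostly on pamrevlumab. Keeping those scores in the primary analysis is a legitimate choice. A reader will still ask what the comparison looks like without such drugs, and the planned answer is weak in two ways.

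First, the split is on behaviour during the trial. If subjects who decline faster are likelier to start another drug, removing users takes the worst outcomes from the faster-declining arm, and the remaining groups are no longer those formed by randomisation. If all users are in one arm, the user stratum has no comparator at all.

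Second, imbalance between arms is what disturbs the comparison, but the trigger counts both arms together.

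The period matters too. SAP 6.4 counts concomitant medication to 60 days after last treatment, and Protocol Appendix 3 allows approved DMD therapies in the extension. Without a stated window, use that began after the Week 52 PUL could be counted.

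**Working it through.** **Inputs.** Difference 2.0, SD 2.9, two-sided alpha 0.05, 1:1 allocation, 92 planned (SAP 3.3); 82 mITT subjects, 97 dosed (SAP section 7). Equal arms of 41 in the mITT are assumed.

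**1. The plan's own figures.** Noncentral t, noncentrality 2.0/(2.9·√(2/n)). With n = 46 per arm: 2.0/0.605 = 3.31, power 90.5%. With n = 41: 2.0/0.640 = 3.12, power 87.0%. The stated 90% and 87% are reproduced.

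**2. The trigger.** Largest number of users not above 10%, and its share of one arm if all are there:

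| Population | 10% | Silent up to | Share of one arm | Fires at |
|---|---|---|---|---|
| 82 | 8.2 | 8 | 8/41 = 19.5% | 9 (22.0%) |
| 92 | 9.2 | 9 | 9/46 = 19.6% | 10 (21.7%) |
| 97 | 9.7 | 9 | 9/48 = 18.8% | 10 (20.8%) |

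Eight of 41 against 0 of 41 has a Fisher exact p of 0.005, yet nothing is run. The unnamed population also matters: 9 users are 11.0% of 82 but 9.3% of 97, so the rule fires on one reading and not on the other.

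**3. What can go unexamined.** Assume 8 users and a drug benefit of g PUL points.

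- All on placebo, true difference 2.0: expected difference 2.0 − (8/41)g = 1.80, 1.61 or 1.41 for g = 1, 2 or 3. Power falls from 87% to 80%, 70% or 59%.
- All on pamrevlumab, which has no effect: rejection rate 6.0%, 9.2% or 14.7%.

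These figures measure the distance from an effect without prohibited drugs. They are not errors in a treatment-policy estimate, which includes such use by design.

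**4. The split when it does run.** Take the smallest count that fires: 9 users, all on placebo, p = 9/41 = 0.2195. Let use come from the low tail of a latent variable with correlation r to the Week 52 change. The non-user placebo mean then rises by SD·r·φ(z)/(1 − p), with z = Φ⁻¹(p) = −0.774, φ(z) = 0.2957 and φ(z)/(1 − p) = 0.379.

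- r = 0.3: 2.9 × 0.3 × 0.379 = 0.33, non-user difference 1.67.
- r = 0.5: 2.9 × 0.5 × 0.379 = 0.55, non-user difference 1.45.
- All data: 2.0 − 0.2195g = 1.78, 1.56 or 1.34 for g = 1, 2 or 3.

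Against a true 2.0, the split is further away than all data at g = 1. At g = 2 it is nearer for r = 0.3 and further for r = 0.5. At g = 3 it is nearer for both.

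A simulation with an inert drug and use in both arms, likelier in faster decliners (13–25% of placebo, 6–13% of pamrevlumab), gave 1.66–1.77 in non-users and 1.48–1.57 in users among trials where the trigger fired. With no treatment effect and the same mechanism in both arms, no bias appeared.

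**5. The alternative.** Simulation with interim visits, 9 placebo users, true difference 2.0, r = 0.3 to 0.5:

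| Use depends on | Non-user split | Imputed after first use |
|---|---|---|
| Observed Week 28 score | 1.70–1.82 | 2.02 |
| Week 52 outcome itself | 1.46–1.68 | 1.66–1.81 |

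Imputation was not worse than the split in either case. It removed the bias only where observed scores explained the use.

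**The case against.** The strongest reply is that this is one conditional, supportive subgroup outside the testing sequence in SAP Table 1, and that much is already in place. Treatment policy settles how scores after use are handled. Important deviations are tabulated, DMD medications are summarised, and data are presented by arm, so an imbalance would be visible whether or not the trigger fires. All of that stands, and it limits the weight of the point.

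A reader might infer that the 10% split is the only analysis bearing on prohibited use. It is not: the per-protocol analysis can exclude users with no threshold. That safeguard is weak. It depends on which deviations are classed as major, it also drops subjects for fewer than 24 doses or early termination, and it too excludes on post-randomisation events.

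A reader might also infer that the rule is silent whenever use is concentrated in one arm. It is silent only up to about 19–20% of one arm with none in the other.

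Nor do the documents show that the split is always worse than the all-data analysis; step 4 shows that this turns on the assumed benefit. The shifts for the split in step 4 (0.33 and 0.55) are below one standard error of the difference, 2.9·√(2/41) = 0.64. That use would be driven by decline is also an assumption. The protocol synopsis contemplates agents gaining marketing authorisation during the trial, which is another route.

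**Conclusion.** The point holds in limited form. Beyond the per-protocol analysis, the plan's response to prohibited DMD drugs is a non-randomised split that may be biased when it runs. Its trigger can stay silent at 19.5% use in one mITT arm against 0% in the other. The set and the period for counting users are undefined.

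A reader might conclude that the primary result or the type I error rate is compromised. The documents do not support that: the treatment-policy estimand includes such use by design, and the split is not tested for a claim.

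The trigger arithmetic rests only on 82 subjects and an even division between arms. Every figure for bias, power or rejection rate rests on assumed use, benefit and correlation, for which the documents give no values. This is a cheap improvement to a supportive analysis, worth making before unblinding.

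**What to change.** Replace the triggered with/without split in SAP 6.6.4 with one supplementary analysis of the primary endpoint under a hypothetical strategy. Run it always, on all mITT subjects as randomised:

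- Set PUL scores after the first prohibited DMD drug to missing.
- Impute them from baseline and earlier PUL visits with the multiple-imputation code in 6.6.1.2.3. Use jump-to-control (6.6.1.2.4) as a second assumption; it adds nothing when users are only on placebo, since they are imputed from placebo either way.
- Compare the result with the 6.6.1.2.3 analysis that keeps scores after use, so that any difference reflects the handling of use and not a change of model.
- Report the number of users and the time of first use by arm, counting use from randomisation to the Week 52 PUL.

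Leave the primary analysis unchanged. The cost is SAP wording and one extra run of planned code. The analysis rests on an untestable imputation assumption, as the other imputation analyses do. It reduces but does not remove bias if use depends on decline not captured by observed scores.

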### **6.7. PK Analyses**

A summary of drug concentrations by visit as well as a listing will be provided. A population PK analysis, as well as an exposure-response analysis, will be defined in a separate PK analysis plan.

### **6.8. Safety Analyses**

#### **6.8.1. Adverse Events**

Adverse events will be coded using MedDRA version 26.0 or higher.

A new or worsening AE occurring on or after the first dose of study medication and within 60 days after the last dose of study drug is defined as a treatment emergent adverse event (TEAE). Partially or incomplete missing AE start/stop date/time will be imputed ([Appendix 1](#)).

If more than one event occurs with the same system organ class (SOC) and preferred term (PT) for the same patient, the patient will be counted only once for that preferred term using the most severe and most related occurrence for the summarization by common terminology criteria for adverse events (CTCAE) severity grade and by relationship to the study medication. Relationship to study drug will be imputed as “Related” for any TEAE with missing value for relationship.

The following summary AE tables including number (%) of subjects will be produced:

- Summary of all AEs
- TEAEs by PT
- TEAEs by SOC and PT
- TEAEs by SOC, PT, and maximum severity
- TEAEs with severity grade  $\geq 3$  by SOC and PT
- TEAEs related to study medication determined by investigator by SOC and PT
- Common TEAEs ( $\geq 5\%$  of subjects in either treatment arm) by SOC and PT
- Common non-serious TEAEs ( $\geq 5\%$  of subjects in either treatment arm) by SOC and PT (Note: this is required for ClinicalTrials.gov)
- TEAEs leading to discontinuation of study medication by SOC and PT
- TEAEs leading to interruption of study medication by SOC and PT
- Treatment-emergent serious AEs (TESAEs) by SOC and PT
- TESAEs by SOC, PT, and maximum severity
- TESAEs related to study medication determined by investigator by SOC and PT
- Fatal TESAEs (i.e., adverse events that has an outcome of death) by SOC and PT
- All cause deaths

Listings of serious adverse events (SAEs), adverse events leading to study drug discontinuation, hypersensitivity, and infusion reactions, and all cause deaths will be provided.

Additionally, the following safety analyses will be conducted:

- Number and percentage subjects with bone fractures
- Ulna length measurements for indirect measure of growth velocity (cm/year) for subjects under the age of 18 (Refer to [Section 6.8.7](#))

Refer to [Section 6.8.6](#) for special safety events such as hypersensitivity reactions and related topics.

**6.8.2. Clinical Laboratory Assessments**

Blood samples are drawn for the following analyses showed in Table 2.

**Table 2: Laboratory Tests**

CBC:	Chemistry Panel:
Absolute neutrophil count (ANC)	BUN
Eosinophils	Creatine Kinase
RBCs (Erythrocyte count)	Creatinine
Hematocrit %	Chloride
Hemoglobin	Magnesium

WBCs (Leukocyte count)	ALP
Lymphocytes	ALT
Monocytes	AST
Neutrophils	Bilirubin, total
Platelets	Albumin
CRP	Phosphorous
Basophils	Potassium
	Sodium
	GGT
	Calcium
	GFR
	Cystatin-C

Laboratory test results and change from baseline are summarized by analysis visit and by treatment arm.

CTCAE grade 3 or higher lab test results will be considered potentially clinically significant. These results are summarized and presented in a data listing.

Shift tables to summarize changes from baseline to each visit in CTCAE v5.0 categories are tabulated. Shift from baseline to most severe CTCAE category during the study is also summarized.

Due to central lab kit shortages caused by Covid-19, lab data may be collected using local labs in lieu of the central lab. The local lab data will be integrated with central lab data, when appropriate and feasible. Sensitivity analyses may be performed for key analyses of lab parameters with and without local lab values (i.e., set to missing).

An eDISH (evaluation of Drug Induce Severe Hepatotoxicity) analytical graph, which is a scatter plot of maximum observed total bilirubin versus maximum observed ALT or AST, will be generated to identify cases in Hy's law range.

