4. SELECTION AND WITHDRAWAL OF SUBJECTS

4.1. Subject Inclusion Criteria

In order to be eligible for inclusion in this trial, a subject must meet all of the following:

Age, Consent, and Contraception

1. Males at least 12 years of age, non-ambulatory at screening initiation
2. Written consent by patient and/or legal guardian as per regional/ country and/or IRB/IEC requirements
3. Male subjects with partners of childbearing potential must use contraception during the conduct of the study, and for 12 weeks after the last dose of study drug.

DMD Diagnosis:

4. Medical history includes diagnosis of DMD and confirmed Duchenne mutation using a validated genetic test

Performance criteria:

5. Brooke Score for Arms and Shoulders ≤ 5
6. Able to undergo MRI test for the upper arm extremities (Biceps Brachii muscle) and cardiac muscle
7. Able to perform spirometry

Pulmonary and Cardiac criteria:

8. Average (of Screening and Day 0) percent predicted FVC between 45 and 85, inclusive
9. Left ventricular ejection fraction $\geq 50\%$ as determined by local cardiac MRI read at screening or within 3 months prior to randomization (Day 0)
10. If subjects have a history of cardiomyopathy, then subject must be on a stable dose of cardiomyopathy/ heart failure medications (e.g., angiotensin converting enzyme inhibitors, aldosterone receptors blockers, angiotensin- receptor blockers, and beta-blockers) for at least 1 month prior to screening. If subjects have no diagnosis of cardiomyopathy, then no dose of cardiomyopathy/heart failure medication is required for eligibility.
11. On a stable dose of systemic corticosteroids for a minimum of 6 months, with no substantial change in dosage for a minimum of 3 months (except for adjustments for changes in body weight) prior to screening. Corticosteroid dosage should be in compliance with the DMD Care Considerations Working Group recommendations (e.g. prednisone or prednisolone 0.75 mg/kg per day or deflazacort 0.9 mg/kg per day) or stable dose. A reasonable expectation is that dosage and dosing regimen would not change significantly for the duration of the study.

Vaccination:

12. Agreement to receive annual influenza vaccinations during the course of the study.

Laboratory criteria:

13. Adequate renal function: cystatin C ≤ 1.4 mg/L
14. Adequate hematology and electrolytes parameters:
 - a. Platelets $>100,000$ /mcL
 - b. Hemoglobin >12 g/dL
 - c. Absolute neutrophil count >1500 / μ L

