 - d. Serum calcium (Ca), potassium (K), sodium (Na), magnesium (Mg) and phosphorus (P) levels are within a clinically accepted range for DMD patients.
15. Adequate hepatic function:
 - a. No history or evidence of liver disease
 - b. Gamma glutamyl transferase (GGT) ≤ 3 x upper limit of
 - c. Total bilirubin ≤ 1.5 xULN

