6.2.3.1. Central Laboratory Evaluations

The following labs will be evaluated by a central laboratory in accordance with the SOA ([Appendix 1](#)):

The total amount of blood to be drawn for routine central laboratory assessments is in [Appendix 2](#). The max total for any blood draw visit is about 1.8 tablespoons (26ml/visit). An additional 1.4 teaspoons (20 ml) will be drawn in the event of an immunogenic reaction (see [Section 6.2.3.2.3](#) for more detail).

Local guidance and regulations on total blood volume to be drawn takes precedence over general recommendations.

Glomerular Filtration Rate (GFR) is calculated and resulted by the central lab contracted by the Sponsor for Exclusion Criteria 5c. For subjects 18 years old and under, the “Creatinine – Cystatin C based CKiD equation (Schwartz 2012)” is used. For subjects 19 years old and above, the “CKD-EPI cystatin C equation (Levey 2009)” is used. However, it is common for patients with DMD to have very low creatinine to the level where it is below detectable limits and a result cannot be reported. As a result, GFR may or may not be available to support the evaluation of acute kidney injury. Other tests and diagnostic tools for assessment by the investigator should be used in this instance.

Table 4: Laboratory Tests

CBC:	Chemistry Panel:
Absolute neutrophil count (ANC)	BUN
Eosinophils	Creatine Kinase
RBCs (Erythrocyte count)	Creatinine
Hematocrit %	Chloride
Hemoglobin	Magnesium
WBCs (Leukocyte count)	ALP
Lymphocytes	ALT
Monocytes	AST
Neutrophils	Bilirubin, total

Platelets	Albumin
CRP	Phosphorous
Basophils	Potassium
	Sodium
	GGT
	Calcium
	GFR
	Cystatin-C
Abbreviations: ALP = alkaline phosphatase; ALT = alanine aminotransferase; AST = aspartate aminotransferase; GGT = Gamma-glutamyltransferase; BUN = blood urea nitrogen; CBC = complete blood count; RBC = red blood cell; WBCs = white blood cells. CRP= C-reactive protein; GFR = Glomerular filtration rate	

Central lab results obtained during the screening period will be used to determine subject eligibility for participation in the trial. Central lab results will be reviewed by the investigator for clinical significance and to determine appropriate reporting of adverse events (see [Section 7.3](#)). A Central Laboratory Manual with instructions on specimen collection, processing, storing, and shipping to the central laboratory will be provided to all participating sites.

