### APPENDIX 4. LABORATORY TEST CTCAE CRITERIA

The following table is extracted from NCI Common Terminology Criteria for Adverse Events (CTCAE) Version 5.0

Chemistry

		Grade 1	Grade 2	Grade 3	Grade 4
Bicarbonate	Decreased	<LLN and no intervention initiated	None	None	None
Creatinine		ULN – 1.5 x ULN	>1.5 – 3.0 x baseline  >1.5 – 3.0 x ULN	>3.0 x baseline  >3.0 – 6.0 x ULN	>6.0 x ULN
Albumin	Decreased	3 g/dL – LLN	2 - <3 g/dL	<2 g/dL	
Alkaline phosphatase (ALP)		ULN – 2.5 x ULN  ; 2.0 - 2.5 x baseline 	>2.5 – 5.0 x ULN  ; >2.5 - 5.0 x baseline 	>5.0 – 20.0 x ULN  ; >5.0 - 20.0 x baseline 	> 20.0 x ULN  ; >20.0 x baseline 
ALT		ULN – 3.0 x ULN  ; 1.5 - 3.0 x baseline 	>3.0 – 5.0 x ULN  ; >3.0 - 5.0 x baseline 	>5.0 – 20.0 x ULN  ; >5.0 - 20.0 x baseline 	>20.0 x ULN  ; >20.0 x baseline 
AST		ULN – 3.0 x ULN  ; 1.5 - 3.0 x baseline 	>3.0 – 5.0 x ULN  ; >3.0 - 5.0 x baseline 	>5.0 – 20.0 x ULN  ; >5.0 - 20.0 x baseline 	>20.0 x ULN  ; >20.0 x baseline 
Total bilirubin		ULN – 1.5 x ULN  ; > 1.0 - 1.5 x baseline 	>1.5 – 3.0 x ULN  ; >1.5 - 3.0 x baseline 	>3.0 – 10.0 x ULN  ; >3.0 - 10.0 x baseline 	>10.0 x ULN  ; >10.0 x baseline 
Calcium (Corrected)	Decreased	8.0 mg/dL – LLN	7.0 - <8.0 mg/dL	6.0 - <7.0 mg/dL	<6.0 mg/dL
		ULN – 11.5 mg/dL	>11.5 – 12.5 mg/dL	>12.5 – 13.5 mg/dL	>13.5 mg/dL
Glucose (Random)	Decreased	55 mg/dL – LLN	40 - <55 mg/dL	30 - <40 mg/dL	<30 mg/dL
Potassium	Decreased	3.0 mmol/L – LLN	3.0 mmol/L – LLN 	2.5 - <3.0 mmol/L	<2.5 mmol/L
		ULN – 5.5 mmol/L	>5.5 – 6.0 mmol/L 	>6.0 – 7.0 mmol/L	>7.0 mmol/L
Sodium	Decreased	130 mmol/L – LLN	125-129 mmol/L and asymptomatic	125-129 mmol/L symptomatic; 120-124 mmol/L regardless of symptoms	<120 mmol/L
		ULN – 150 mmol/L	>150 – 155 mmol/L 	>155 – 160 mmol/L	>160 mmol/L
Magnesium	Decreased	1.2 mg/dL – LLN	0.9 - <1.2 mg/dL	0.7 - <0.9 mg/dL	<0.7 mg/dL

		ULN – 3.0 mg/dL	None	>3.0 – 8.0 mg/dL	>8.0 mg/dL
--	--	-----------------	------	------------------	------------

Serum Hematology

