		Grade 1	Grade 2	Grade 3	Grade 4
Hemoglobin	Decreased	10.0 g/dL – LLN	8.0 - <10.0 g/dL	<8.0 g/dL	
		>0 – 2 g/dL	>2 – 4 g/dL	>4 g/dL	
Platelet	Decreased	75,000 /mm  – LLN	50,000 – <75,000 /mm 	25,000 - <50,000 /mm 	<25,000 /mm 
WBC	Decreased	3,000 /mm  – LLN	2,000 - <3,000 /mm 	1,000 - <2,000 /mm 	<1,000 /mm 
		None	None	>100,000 /mm 	
aPTT		ULN – 1.5 x ULN	>1.5 – 2.5 x ULN	>2.5 x ULN	
Lymphocytes	Decreased	800 /mm  – LLN	500 - <800 /mm 	200 - <500 /mm 	<200 /mm 
		None	>4,000 – 20,000 /mm 	>20,000 /mm 	
Neutrophils	Decreased	1500 /mm  - LLN	1000 - <1500 /mm 	500 - <1000/mm 	<500/mm 
Eosinophils		>ULN and >Baseline	None	Steroids initiated	None

Decreased: below LLN; Otherwise, above ULN;

[1] Symptomatic, Intervention indicated

[2] Baseline is used if it is above ULN

[3] Intervention indicated

[4] ULN is used if Baseline was normal

[5] Baseline is used if Baseline was abnormal

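### The SAP's CTCAE-based laboratory flag covers kidney function by creatinine alone and gives cystatin C, GFR and GGT no pre-specified subject-level flag, shift table or count by arm

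*SAP*

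**What the plan says.** **The flag.** SAP 6.8.2 says that "CTCAE grade 3 or higher lab test results will be considered potentially clinically significant". Those results are summarized and listed. Shift tables, by visit and to the worst category on study, also use CTCAE v5.0 categories.

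**The grades.** SAP Appendix 4 introduces its criteria with "The following table is extracted from NCI Common Terminology Criteria for Adverse Events (CTCAE) Version 5.0". For kidney function it grades creatinine only. Grade 3 is above 3 x ULN, and the baseline multiple has the note "Baseline is used if it is above ULN". For the liver it grades ALT, AST, ALP and total bilirubin, where the note is "Baseline is used if Baseline was abnormal". Cystatin C, GFR and GGT have no row, although SAP Table 2 lists all three.

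**The liver plot.** SAP 6.8.2 also plans an eDISH graph, "a scatter plot of maximum observed total bilirubin versus maximum observed ALT or AST".

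**The protocol's own markers.** Section 4.1 criterion 13 reads "Adequate renal function: cystatin C", with a limit of 1.4 mg/L. Criterion 15 uses GGT (3 x ULN) and total bilirubin (1.5 x ULN) and sets no ALT or AST limit. Exclusion 5c uses GFR below 30 mL/min/1.73 m². On creatinine, Protocol 6.2.3.1 says "it is common for patients with DMD to have very low creatinine to the level where it is below detectable limits", and it warns that GFR may therefore be unavailable.

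**The concern.** Clinically significant laboratory abnormalities are a named safety assessment in both documents (Protocol 3.1.1.3, SAP 4.3). The rule that picks them out should therefore work for the markers the protocol relies on in this disease. As written, the kidney is judged by the one marker that the protocol itself calls often undetectable, against a limit tied to ULN. The marker used for renal entry has no criterion. GGT is in the same position for the liver: it is an entry criterion, and SAP 5.5 names it among the liver function tests, but it has no grade in Appendix 4.

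At stake is how a table with few or no renal flags would be read. It could look like evidence of renal safety when it mainly reflects how hard the criterion is to meet. The report would also hold no planned count, by arm, of subjects whose cystatin C or GGT rose past a stated limit.

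**Working it through.** The plan states no figure to reproduce here. The check is a cross-match of two tables, then arithmetic on the Appendix 4 thresholds.

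**1. Coverage.** SAP Table 2 has 17 chemistry tests.
- With a row in Appendix 4 (10): creatinine, magnesium, ALP, ALT, AST, total bilirubin, albumin, potassium, sodium, calcium.
- Without a row (7): BUN, creatine kinase, chloride, phosphorous, GGT, GFR, cystatin C.
- Rows for tests that Table 2 does not list (3): bicarbonate, glucose, aPTT.

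So creatinine is the only kidney-function marker graded, and the grading table was not matched to this trial's panel.

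**2. Rise in creatinine needed for each grade.** With baseline at or below ULN, only the ULN multiples apply. Let baseline = f x ULN. The fold rise needed is the threshold (in ULN multiples) divided by f. The thresholds are 1 (grade 1), 1.5 (grade 2) and 3 (grade 3). The documents give no baseline creatinine, so f is assumed.

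| Assumed f | Grade 1: 1/f | Grade 2: 1.5/f | Grade 3: 3/f |
|---|---|---|---|
| 1 | >1 | >1.5 | >3 |
| 1/2 | >2 | >3 | >6 |
| 1/3 | >3 | >4.5 | >9 |
| 1/5 | >5 | >7.5 | >15 |

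At one third of ULN, a tripling only reaches ULN and earns no grade. The flag needs more than a 9-fold rise, and at one fifth of ULN more than a 15-fold rise.

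**3. Undetectable values.** SAP 5.3.4 replaces a result below a limit X by X in summary statistics. The true baseline is then lower than the value used, so any computed rise from it is a lower bound.

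**4. The ungraded markers.** A cystatin C that doubles from 1.2 to 2.4 mg/L (illustrative) ends at 2.4/1.4 = 1.7 times the entry limit. Appendix 4 assigns it no grade, so it enters neither the flag nor a shift table built on Appendix 4. The same is true of a GGT above 3 x ULN.

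**5. A model inside the same SAP.** For vital signs, SAP 6.8.3 and Table 3 set an observed-value limit and a change from baseline (both needed, except for weight), and count the subjects who meet them by arm. Cystatin C and GGT have nothing comparable.

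**The case against.** The strongest reply is that the data are not hidden, and it is largely right. A reader might infer that organ toxicity could go undetected; the documents do not support that. SAP 6.8.2 summarizes the Table 2 tests and their changes by visit and arm, and SAP 5.1.2 includes the minimum and maximum. SAP 5.5 takes the maximum GGT within a visit window, and SAP 5.1 lists all data. Protocol 7.3.7 has investigators review every central result and report clinically significant ones as AEs, and a DMC reviews safety data (SAP 5.4). What survives is narrower. A maximum shows one extreme value, not how many subjects crossed a limit in each arm, and the AE route depends on judgement and on a need for active management.

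Other limits also stand:
- SAP 6.8.2 refers to CTCAE without restricting itself to Appendix 4, which calls itself an extract. The absence of a criterion is shown for the SAP, not for CTCAE as a whole. If CTCAE does grade any of these tests, Appendix 4 is incomplete; if not, a criterion is missing. Either way the SAP needs a statement.
- The shift tables use all grades, so creatinine changes short of grade 3 can appear there, from the fold rises in the table above.
- A reader might infer that ALT and AST cannot separate muscle from liver injury here. The documents do not say so. ALT and AST are graded against an abnormal baseline, ALP and bilirubin are graded too, and bilirubin is an eDISH axis. There is no basis here for changing that plot.
- A reader might take Protocol 6.2.3.1 as the reason for the cystatin C criterion. It discusses GFR for exclusion 5c and gives no reason for criterion 13.
- GFR is a weak substitute at 18 and under, because its equation uses creatinine. From 19 it uses cystatin C alone.
- Entry limits were not written as toxicity thresholds. Used alone, 1.4 mg/L would flag a move from 1.39 to 1.41.

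**Conclusion.** The point holds as a gap in planned safety reporting. The renal flag in the SAP rests on creatinine alone and is insensitive when baseline is low: more than 9- to 15-fold for grade 3 at an assumed one third to one fifth of ULN, and more than 6-fold even at one half. That baseline range is an assumption; the direction rests on the protocol's own statement that creatinine is commonly undetectable. Cystatin C, GFR and GGT have no pre-specified subject-level flag, shift table or by-arm count in the SAP.

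The renal half is the stronger one. On the liver side the finding is only that GGT, an entry criterion and a named liver test, has no criterion. Efficacy conclusions and the collection of safety data are unaffected. What is affected is how much reassurance a short list of flagged laboratory results can give.

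**What to change.** Before unblinding, amend SAP 6.8.2 and Appendix 4 as follows.

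1. **Cystatin C and GGT:** add a reporting flag, a shift from baseline and a count of subjects by arm. Candidate thresholds are the protocol's entry limits (above 1.4 mg/L; above 3 x ULN), combined with a change-from-baseline condition in the manner of Table 3. The clinical team should confirm the cut-offs and set the size of the change.
2. **Creatinine:** add a criterion relative to baseline, and state how a baseline below the detection limit is handled.
3. **GFR:** report it as secondary where available, with exclusion 5c's 30 mL/min/1.73 m² as a candidate limit and the number of subjects with a reportable value in each arm.
4. **Appendix 4:** state whether grading is limited to this table, and remove or explain the rows for bicarbonate, glucose and aPTT.

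These are reporting thresholds only and change no patient management. The data are already collected, so the cost is SAP wording and a few extra tables. The downside is some flags for small crossings of a limit, which the change condition should reduce.
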